4.4 MEDICAL HISTORY

Medical history data will consist of significant conditions or diseases recorded during the screening process. Data will be tabulated using the MedDRA primary system organ class (SOC) and preferred term for subjects in the safety population.

4.5 STUDY DRUG EXPOSURE AND COMPLIANCE

Study drug exposure and duration in the study will be derived based on first and last dose taken. Compliance will be computed as percentage of medication taken.

4.6 EFFICACY ANALYSIS

Two patient populations, one with both narcolepsy symptoms (EDS and cataplexy) and one with only EDS will be studied in a single parallel groups, dose-escalation design. The treatments are placebo and increasing doses of the test drug, FT218. Two primary outcome measures, MWT and CGI quantify the treatment effect on EDS and the NCA is the primary

outcome measure for cataplexy. All ITT or PP subjects will be included in the evaluation of EDS and all ITT or PP subjects with both conditions will be used in the evaluation of cataplexy.

Subject demographics and baseline characteristics will be tabulated for all randomized subjects. The baseline comparability of treatment groups with respect to subject demographics and baseline characteristics will be described, but formal statistical tests will not be performed.

4.6.1: PRIMARY ANALYSIS:

A mixed effect repeated measures (MMRM) means model will be used to analyze change from baseline for MWT and cataplexy. Each model will include treatment, time (at which the measurement was taken), treatment-by-time interaction, site and baseline score as fixed effects and subjects as random effects. In fitting the model, time will range over the entire period of observations.

For CGI, a GLIMMIX model for binomial data with logit link will be used instead of a MMRM to analyze the categorized CGI response, i.e., proportion of patients who were very much or much improved. The observed values for the categorized response (very much or much improved versus other category) will be used as responses in the model. Each model will include treatment, time (at which the measurement was taken), treatment-by-time interaction and site as fixed effects and subjects as random effects. In fitting the model, time will range over the entire period of observations. The odds ratio, 95% confidence intervals for the odds ratio and p-value will be provided.

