Efficacy assessments include MWT, CGI, Sleep and Symptom Daily Diary, nocturnal PSG, and ESS

Safety:

Safety assessments include AEs, laboratory parameters, vital signs, physical examination, 12-lead electrocardiogram, Columbia-Suicide Severity Rating Scale

Statistical Analysis:

A mixed-effects means model with repeated measures (MMRM) will be used to analyze change from baseline for each of the coprimary endpoints. Each model will include treatment, time, treatment-by time interaction, site and baseline score as fixed effects and subjects as random effects. [REDACTED]

The primary hypothesis tests of the efficacy of individual doses will be performed as contrasts within the mixed models. The hypothesis testing will proceed in the following order: first, to test hypotheses for EDS, both MWT and CGI will be examined for statistical significance for the 9.0 g dose using the data collected during Periods 3c(i), and 3c(ii). If both tests are significant, NCA for the same dose will be tested. If the first test fails (either MWT or CGI not significant), the data for the 9.0 g dose was not able to reject the null hypothesis of equality to placebo for either symptom. If the first test is significant (both MWT and CGI significant) but the second test (NCA) fails, the dose has been demonstrated to exceed placebo for EDS treatment but not for cataplexy. If both tests are statistically significant, the dose has been shown to be effective for EDS and cataplexy.

If the 9.0 g dose demonstrates efficacy for both EDS and cataplexy, the same sequence of testing will be followed for the 7.5 g dose using the data collected during Periods 3b(i) and 3b(ii). If the 7.5 g dose demonstrates efficacy for both EDS and cataplexy, the same sequence of testing will be followed for the 6 g dose using the data collected during Period 3a.

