9.1.2 Period 2: Visit 2 (Week -1, Day 7) Baseline Visit

Following the screening visit, the second stage of subject assessment for continued eligibility will occur at the baseline visit i.e. Visit 2.

At this visit the PI/designee will firstly assess for:

- Confirmation of continued eligibility
- Compliance with drug washout requirements
- Assess compliance with alcohol consumption, abstinence from alcohol, and all other study restrictions (study restriction questions)
- Assess drug abuse and dependence. Clinical judgement to be exercised in determining need for performing additional urine drug screen for benzodiazepines, cannabis, cocaine, opiates and barbiturates at this visit

- Compliance in completing the screening/baseline Sleep and Symptom Daily Diary. Compliance is defined as completing the diary at least 4 times in each of the screening weeks.
 - Confirmation of continued presence of cataplexy (NT1 subjects only) as defined by an average of 8 reported cataplexy attacks per week as reported in the Sleep and Symptom Daily Diary
- EDS as defined by a baseline ESS score > 10 points

If these criteria are met the following assessments and procedures will occur:

- Review and record all concomitant medication
 - Assess for adherence to prohibited medication requirements
- Document any AEs
- Complete baseline CGI assessment of severity of sleepiness (by investigator)
- Administer baseline C-SSRS questionnaire
- Perform complete physical exam if determined clinically indicated by the PI
- Record vital signs (systolic and diastolic BP, heart rate)
- Collect samples for hematology and biochemistry
- Collect sample for urinalysis
- Perform urine pregnancy test (female subjects)
- Update the IRT system with planned Visit 3 date

If all assessments are satisfactory the study subject will then progress to having overnight 8-hour PSG with next-day 5 hour nap MWT. Results will be reported from the central scoring laboratory ([Section 11.12](#)).

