Visit 4 includes a full efficacy assessment (evaluation of the 6.0 g efficacy). Procedures at this visit include:

- Compliance with drug washout requirements
- Confirmation of continued eligibility
- Assess study restrictions compliance: (i) abstinence from alcohol, (ii) smoking restrictions, and (iii) all other study restrictions
- Assess for drug abuse and dependence. Clinical judgement to be exercised in determining need for performing urine drug screen for benzodiazepines, cannabis, cocaine, opiates, and barbiturates
- Assess compliance with drug handling, management, and safety requirements
 - Confirm subject is adhering to requirement to eat at least 2 hours before taking study drug
 - Subject re-education on study drug safety and handling and study-related procedures if deemed necessary by PI
- Review and record of concomitant medication
 - Assess for adherence to prohibited medication requirements.
- Document any AEs
- Collect CGI assessment of improvement in sleepiness (investigator blinded to MWT results)
- Administer "since last visit" C-SSRS questionnaire
- Perform physical examination if determined clinically indicated by the PI
- Record vital signs (systolic and diastolic BP and heart rate)
- Perform urine pregnancy test (female subjects)
- Review and confirmation of ePRO diary and questionnaire completion (on subject questioning and ePRO check).
 - Self-recorded study drug compliance record (with returns check)

- Compliance with Sleep and Symptom Daily Diary completion requirements for the past 3-week period. Completion of ESS (subject questionnaire)
- Overnight PSG
 - Next-day 5 hour nap MWT
- Dispense drug and perform accountability
- ePRO device handling and ePRO completion requirements and consequences of poor compliance will be discussed again with the study subject
 - Study subjects will be instructed to complete their Sleep and Symptom Daily Diary on a daily basis for the next 2 weeks

If the PI is concerned that the study subject will be unable to comply with FT218 study drug and study requirements following training and education session the subject will be informed and withdrawn from study.

- Schedule Visit 5 with the study subject
- Update IRT system with subject's details for next visit and study drug returns

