9.2.6 Period 3c(iii) Visit 8 (Week 13, Day 7) End of Study (EOS)

This visit includes a full efficacy assessment (evaluation of the 9.0 g efficacy).

- Compliance with drug washout requirements
- Confirmation of continued eligibility
- Assess study restrictions compliance: (i) abstinence from alcohol, (ii) smoking restrictions, and (iii) all other study restrictions
- Assess drug abuse and dependence. Clinical judgement to be exercised in determining need for performing urine drug screen for benzodiazepines, cannabis, cocaine, opiates and barbiturates
- Assess compliance with drug handling, management and safety requirements
 - Confirm subject is adhering to requirement to eat at least 2 hours before taking study drug
- Review and record of concomitant medication
 - Assess for adherence to prohibited medication requirements
- Document any AEs

- Complete CGI assessment of improvement in sleepiness (investigator blinded to MWT results)
- Administer “since last visit” C-SSRS questionnaire
- Perform full physical examination
- Collect weight
- Collect vital signs (systolic and diastolic BP and heart rate)
- Collect samples for hematology, biochemistry, and perform urine pregnancy test (female subjects)
- Collect sample for urinalysis
- Perform 12-lead ECG after subject is supine for 5 minutes
- Review and confirmation of ePRO diary and questionnaire completion: (on subject questioning and ePRO check)
 - Self-recorded study drug compliance record (with returns check)
 - Compliance with Sleep and Symptom Daily Diary completion requirements for the past 3-week period. Completion of ESS (subject questionnaire)
- Overnight PSG
 - Next-day 5 hour nap MWT
- Perform drug accountability and reconciliation
- Update IRT system with EOS details and final subject drug accountability
- Obtain ePRO device from subject and place in on-site safe storage
- Schedule follow-up visit with study subject

9.3 Follow-up Period – Period 4

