10.1.1.2 Clinical Global Impression of Sleepiness

At Visit 2, the CGI assessment of severity of sleepiness scale will be conducted. At subsequent assessments, the CGI is evaluated on a 7-point scale, centered at No Change, and ranging from Very Much Worse to Very Much Improved. Subjects are rated by the qualified and approved evaluators who based their assessments on the severity of sleepiness at baseline.

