11.9.1.1 Primary Analysis

A mixed-effects means model with repeated measures will be used to analyze change from baseline for each of the MWT and cataplexy endpoints. Each model will include treatment, time (at which the measurement was taken), treatment-by-time interaction, site and baseline score as fixed effects, and subjects as random effects. [REDACTED]

For CGI, a GLIMMIX model for binomial data with logit link will be used instead of a MMRM to analyze the categorized CGI response, i.e., proportion of patients who were very much or much improved. The observed values for the categorized response (very much or much improved versus other category) will be used as responses in the model. Each model will include treatment, time (at which the measurement was taken), treatment-by-time interaction and site as fixed effects and subjects as random effects. In fitting the model, time will range over the entire period of observations. The odds ratio, 95% confidence intervals for the odds ratio and p-value will be provided.

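### The CGI co-primary model omits the baseline CGI-S already collected at Visit 2, a modest loss of efficiency at the first testing gate, and the synopsis gives CGI a different model from the Protocol body and SAP

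*SAP*

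**What the plan says.** **CGI model.** Protocol 11.9.1.1 states: "For CGI, a GLIMMIX model for binomial data with logit link will be used instead of a MMRM". The response is binary: the top two improvement categories against all others. SAP 4.6.1 has the same paragraph and gives the model terms as: "Each model will include treatment, time (at which the measurement was taken), treatment-by-time interaction and site as fixed effects and subjects as random effects".

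**MWT and cataplexy model.** The paragraph just before it in SAP 4.6.1 specifies an MMRM on change from baseline with "treatment-by-time interaction, site and baseline score as fixed effects and subjects as random effects". The only difference in the fixed effects is the baseline score.

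**What is collected.** Protocol 10.1.1.2: "At Visit 2, the CGI assessment of severity of sleepiness scale will be conducted". The Visit 2 procedures in Protocol 9.1.2 list it as well: "Complete baseline CGI assessment of severity of sleepiness (by investigator". From Visit 4 on, the rating is improvement (CGI-I): "Collect CGI assessment of improvement in sleepiness" in Protocol 9.2 and "Complete CGI assessment of improvement in sleepiness" at Visit 8 in Protocol 9.2.6. The CGI-I form in Protocol 17.6 asks for a comparison with baseline.

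**Synopsis.** The Statistical Analysis part of Protocol section 3 has one model for everything: "MMRM) will be used to analyze change from baseline for each of the coprimary endpoints", with baseline score among the fixed effects.

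**The concern.** Two things stand out. First, a baseline severity rating is taken on every subject and then not used in the analysis of the endpoint it relates to, while the neighbouring model adjusts for baseline. The visible text gives no reason, and neither CGI paragraph shows a redaction.

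The place matters. Under SAP 4.6.2, MWT and CGI must both be significant at 9 g before cataplexy is tested at that dose, and 7.5 g and then 6 g are reached only after that. If CGI misses at 9 g, everything below it goes untested. Power lost on this one test is therefore lost for the whole sequence.

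Second, a plan prepared for a Special Protocol Assessment (Protocol 11.1, SAP 1.2) states two different primary analyses for one co-primary endpoint.

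**Working it through.** The public text has no CGI power calculation, so there is no stated figure to reproduce. The check is a reading of the text, followed by sizing under assumptions.

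**Step 1: the texts side by side.**

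| | Response | Baseline term |
|---|---|---|
| SAP 4.6.1 and Protocol 11.9.1.1, MWT and cataplexy | change from baseline, MMRM | yes |
| SAP 4.6.1 and Protocol 11.9.1.1, CGI | binary responder, logit mixed model | no |
| Protocol synopsis, all co-primaries | change from baseline, MMRM | yes |

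For CGI, a change from baseline would need either CGI-S repeated after Visit 2 or a baseline value of CGI-I. The visit lists for Visits 4 to 8 contain only CGI-I, which has no baseline value to subtract. The synopsis row therefore conflicts with the CGI row and does not match the data collected.

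**Step 2: size in the repeated-measures model.** All inputs except allocation, the number of centres and the number of CGI visits are assumptions.

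- From the documents: 1:1 allocation (Protocol 8.4.9), about 60 centres (synopsis), five post-baseline CGI visits (Visits 4 to 8), two-sided 0.05.
- Assumed: N=200, placebo response 25%, total between-subject SD 2 logits (including site SD 0.5 and the CGI-S effect), CGI-S ratings 3 to 7 around 5, complete data.
- Contrast: mean of Visits 7 and 8, z test, 1,500 simulated trials per cell, each data set fitted with and without CGI-S.
- Treatment effect: conditional log odds ratio about 1.18, chosen to give about 80% power in a comparison fit with a random site effect. The SAP has site as a fixed effect. With that, power before adding CGI-S is 72.7 to 74.5% under pseudo-likelihood, and this is the base for the gains below.

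| CGI-S effect (logit per SD) | Power as written, % | Power with CGI-S, % | Gain, points |
|---|---|---|---|
| 0 | 74.5 | 74.3 | -0.1 (before rounding) |
| 0.35 | 73.7 | 73.9 | +0.2 |
| 0.7 | 73.5 | 75.7 | +2.2 |
| 1.0 | 72.7 | 79.1 | +6.4 |

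The Monte Carlo standard error of the paired gains is 0.3 to 0.9 points, so the first two rows cannot be told from zero. At 0.7 logit per SD, changing one assumption at a time (N=150 or 260, about 90% power, site-stratified randomization, subject SD 1.5, placebo response 15%, 40 sites) moves the pseudo-likelihood gain between +0.8 and +3.8 points.

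With 4,000 null trials, type I error goes from 5.1% without CGI-S to 4.5% with it. Under quadrature maximum likelihood the gains are -0.2 / +0.5 / +1.7 / +5.4, but that fixed-site fit rejects 7.4% of null trials with or without CGI-S. Those gains are supportive only; they are not gains at the 5% level.

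**Step 3: a simpler independent check.** One time point, ordinary logistic regression, Wald test, 4,000 trials per setting. Per-arm size for 80% power:

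n = [1.960·√(2p̄(1−p̄)) + 0.8416·√(p₀(1−p₀)+p₁(1−p₁))]² / (p₁−p₀)²

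- 30% vs 50%: (1.960·√0.48 + 0.8416·√0.46)² / 0.04 = 93.0, so 93 per arm.
- 20% vs 40%: (1.960·√0.42 + 0.8416·√0.40)² / 0.04 = 81.2, so 82 per arm.

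| Correlation of baseline with latent response | 30% vs 50%: unadjusted → adjusted, % | 20% vs 40%: unadjusted → adjusted, % |
|---|---|---|
| 0 | 79.5 → 79.5 | 80.9 → 80.4 |
| 0.2 | 80.7 → 82.1 | 81.4 → 81.8 |
| 0.3 | 80.0 → 82.5 | 80.6 → 82.6 |
| 0.5 | 79.8 → 86.8 | 81.5 → 86.1 |

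Null rejection is 4.4 to 5.3% throughout, adjusted or not. The pattern matches step 2: nothing at zero correlation, 0 to 3 points at 0.2 to 0.3, and 5 to 7 points at 0.5.

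**The case against.** The strongest defence is that the two models differ for a reason. MWT and cataplexy are change scores with a baseline on the same measure. CGI-I has none; CGI-S is a different scale, and raters already judge improvement against baseline severity. The unadjusted test is valid under randomization, and no document says how far CGI-S predicts response. Adding it is then a matter of preference, for a gain that may be about 2 points or nothing, in a model already put forward for agency agreement.

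Most of this stands, and it limits the point to efficiency. It does not remove it. Anchoring a rating to baseline does not make the chance of being rated much improved independent of starting severity. MWT change is also measured from baseline, and its model still adjusts.

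Three stronger readings are tempting and are not supported:

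- *The CGI test is biased or invalid.* It is not. Leaving out a prognostic baseline covariate costs power; it does not inflate type I error.
- *The synopsis model cannot be fitted to CGI at all.* CGI-I is itself a rating against baseline and could be entered in an MMRM with CGI-S as baseline score. What cannot be formed is a CGI-S difference or a CGI-I baseline value. A redaction also follows the synopsis model text and might hold a qualifier, although the visible sentence covers every co-primary.
- *The plan has no rule for small sites, no estimation method and no stratification factors.* The randomization sections (Protocol 11.2.2, SAP 2.5) and other statistical text are redacted. Absence from the public text is not absence from the plan, so no criticism is made here.

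**Conclusion.** The point holds as a recommended improvement. Both documents leave baseline CGI-S out of the CGI model, and the value is already collected. The gain at N=200 is about 0 points if CGI-S is weakly or not prognostic, about 2 if moderately prognostic (0.7 logit per SD) and about 5-6 if strongly prognostic (1.0 logit per SD), from a pseudo-likelihood base of about 73-74%. These sizes depend on assumed sample size, response rates, variances and prognostic strength; only the direction and the near absence of a downside are firm. Confidence in the size is medium at best.

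The synopsis conflict is definite on the visible text but small in consequence. The Protocol body and the SAP agree, so a reader should not infer that the choice of CGI model is open.

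**What to change.** 1. In SAP 4.6.1 and Protocol 11.9.1.1, add Visit 2 CGI-S as a fixed effect in the CGI logit mixed model. State whether it enters as linear or categorical, and give a rule for a subject without a Visit 2 rating. If the sponsor prefers to leave it out, record the reason.
2. State that the reported odds ratio, already conditional on subject and site, is then also conditional on baseline severity.
3. In the synopsis, limit MMRM on change from baseline to MWT and cataplexy, and give the binomial mixed model for CGI.

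Cost: wording only, with no new data. Items 1 and 2 change a primary model prepared for a Special Protocol Assessment, so they have to be agreed with the agency and fixed before unblinding. If CGI-S turns out not to be prognostic, the simulated change in power for the fixed-site model is -0.1 points (pseudo-likelihood) or -0.2 (quadrature). Item 3 has no downside.

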4.6.2 SEQUENTIAL TESTING APPROACH FOR COMPARING SOCR AND PLACEBO

The primary hypothesis tests of the efficacy of individual doses will be performed as contrasts within the mixed models. The hypothesis testing will proceed in the following order, which is represented pictorially in Figure 1. First to test hypotheses for EDS, both MWT and CGI will be examined, in parallel for statistically significant differences from placebo for the 9 g dose. The order of hypothesis testing and the tests to be performed are displayed in Figure 1. For the 9 g dose, if both tests are significant, NCA for the same dose will be tested. If the first test fails (either MWT or CGI not significant), the data for the 9 g dose was not able to reject the null hypothesis of equality to placebo for either symptom. If the first test is significant (both MWT and CGI significant,) but the second test (NCA) fails, the 9 g dose has been demonstrated to exceed placebo for EDS treatment but not for cataplexy. If both tests are statistically significant, the 9 g dose has been shown to be effective for EDS and for cataplexy. Although all data are included in the full model, the tests for the 9 g dose are contrasts over the Periods 3c(i) and 3c(ii).

[figure not shown]
If the 9 g dose demonstrates efficacy for both EDS and cataplexy, the same sequence of testing will be followed for the 7.5 g dose using contrasts over the Periods 3b(i) and 3b(ii). If the 7.5 g dose demonstrates efficacy for both EDS and cataplexy, the same sequence of testing will be followed for the 6 g dose using contrasts over Period 3a.

Each dose will be tested at the two-sided alpha level of .05. Efficacy tests for MWT and for CGI within a dose need not be adjusted, since both are required for demonstrating efficacy for EDS at that dose. Efficacy tests for NCA within a dose for demonstrating efficacy for cataplexy also need not be adjusted because the test is reached via a step down procedure. Within each arm, rejection terminates all subsequent hypothesis tests, which will be deemed to be non-significant. A strictly exploratory analysis examining secondary/exploratory endpoints is also proposed to provide evidence of consistency. The Type I error rate for these endpoints will all be tested at the alpha level of .05.

N.B. The testing of the efficacy of the 6 g dose is intended to address the question of identifying the minimally effective dose. If the 9 g dose and then the 7.5 g dose is effective on the primary outcome variables, hypothesis tests on the efficacy of the 6 g dose will be carried out.

Figure 1

4.7 SAFETY ANALYSES

Safety evaluations will be performed on the safety population using the actual treatment administered.

Adverse events will be identified as treatment-emergent (TEAE) if the event occurs or increases in severity after the first dose of study medication is taken. Adverse events will be identified as mild, moderate or severe and related to the treatment as reported on the CRF. The adverse events will be assigned a preferred term (PT) and a system organ class (SOC) according to the Medical Dictionary for Regulatory Activities (MedDRA), latest version. In counting the number of events reported, a continuous event, i.e., an event reported more than once and which did not cease, will be counted only once with the worst recorded severity. Non-continuous AEs reported multiple times by the same subject will be counted as multiple events. AEs will be assigned to the period of the study corresponding to the time of onset. Events presenting immediately prior to the first dose of study medication that do not worsen in severity, will not be included. In deriving the tabulation relating to preferred term reporting, the severity of a recurrent AE will be taken to be the most severe and the relationship to study medication as the most probable within the relevant period of the study. Total exposure to FT218 will be determined in terms of number of days and dose.

Laboratory data will be summarized in terms of the proportions of patients with clinically notable abnormalities using normal ranges. Shift tables will tabulate baseline to most extreme post baseline values. Summary statistics of raw data and change from baseline values will be obtained including means, medians, standard deviations and ranges will be produced.

The summaries will include subjects in the safety population who have had at least one laboratory test performed after the first study drug administration with an available baseline laboratory value. Baseline values will be measured as the last available measure before taking study drug.

[REDACTED]

[REDACTED]

[REDACTED]

[REDACTED]

[REDACTED]

[REDACTED]

[REDACTED]

[REDACTED]

[REDACTED]

[REDACTED]

[REDACTED]

[REDACTED]

[REDACTED]

[REDACTED]

[REDACTED]

[REDACTED]

[REDACTED]

[REDACTED]

[REDACTED]

[REDACTED]

[REDACTED]

[REDACTED]	[REDACTED]	[REDACTED]
[REDACTED]	[REDACTED]	[REDACTED]
[REDACTED]	[REDACTED]	[REDACTED]
[REDACTED]	[REDACTED]	[REDACTED]
[REDACTED]	[REDACTED]	[REDACTED]
[REDACTED]	[REDACTED]	[REDACTED]
[REDACTED]	[REDACTED]	[REDACTED]
[REDACTED]	[REDACTED]	[REDACTED]
[REDACTED]	[REDACTED]	[REDACTED]
[REDACTED]	[REDACTED]	[REDACTED]

[REDACTED]

[REDACTED]

[REDACTED]	[REDACTED]	[REDACTED]	[REDACTED]	[REDACTED]	[REDACTED]	[REDACTED]
[REDACTED]	[REDACTED]	[REDACTED]	[REDACTED]	[REDACTED]	[REDACTED]	[REDACTED]
[REDACTED]	[REDACTED]	[REDACTED]	[REDACTED]	[REDACTED]	[REDACTED]	[REDACTED]
[REDACTED]	[REDACTED]	[REDACTED]	[REDACTED]	[REDACTED]	[REDACTED]	[REDACTED]
[REDACTED]	[REDACTED]	[REDACTED]	[REDACTED]	[REDACTED]	[REDACTED]	[REDACTED]

[REDACTED]

[REDACTED]

[REDACTED]	[REDACTED]	[REDACTED]
[REDACTED]	[REDACTED]	[REDACTED]
[REDACTED]	[REDACTED]	[REDACTED]
[REDACTED]	[REDACTED]	[REDACTED]
[REDACTED]	[REDACTED]	[REDACTED]
[REDACTED]	[REDACTED]	[REDACTED]
[REDACTED]	[REDACTED]	[REDACTED]
[REDACTED]	[REDACTED]	[REDACTED]

[REDACTED]

[REDACTED]

[REDACTED]

[REDACTED]

[REDACTED]

[REDACTED]

[Redacted text block]

[Redacted text block]

[Redacted text block]

[Redacted text block]
